6.4.7 CONCOMITANT MEDICATIONS/TREATMENTS

All medications (prescription and nonprescription) taken at the time of Screening and ongoing from signing of the informed consent to study discharge that do not affect a subject’s eligibility for participation (see [Section 4.2](#)) must be recorded on the case report forms (CRFs).

Actual or estimated start and stop dates must be provided. This information will be obtained from the subject and abstracted from any available medical records. The indication for the medication, dose, and dose regimen will be documented.

Therapy considered necessary for the subject’s welfare may be given at the discretion of the Investigator. If the permissibility of a specific medication/treatment is in question, please contact the Sponsor.

The decision to administer a prohibited medication/treatment ([Section 6.4.8](#)) is made with the safety of the clinical trial subject as the primary consideration. When possible, the Sponsor should be notified before the prohibited medication/treatment is administered.

6.4.8 RESTRICTIONS

Participants should refrain from becoming pregnant until 3 months following the last dose of investigational product by using appropriate contraceptive measures (see [Section 4.1](#)).

Participants must not be vaccinated (e.g., influenza vaccine, COVID-19 vaccine) from 30 days prior to Day 0 until after completion of the study visit 2 weeks after the second dose of investigational product (i.e. the Week 6 visit if the second dose is at Week 4 and the Week 10 visit if the second dose is at Week 8). For Part 2B, receipt of other vaccinations is also prohibited from 2 weeks prior to the Week 48 visit through the Week 50 visit.

Participants must not receive a course of systemic corticosteroids (≥ 2 mg/kg of prednisone or equivalent for 5 days) within 3 months prior to any dose of investigational product.

Participants must not have fever (oral temperature >38.0 degrees Celsius or 100.4 degrees Fahrenheit) within 72 hours prior to each dose of investigational product.

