- g. Serum pregnancy test at screening. Urine pregnancy test at other visits.
- h. INO-4700 or placebo is prepared by unblinded pharmacy personnel. All doses delivered via ID injection followed by EP.
- i. For Study Groups A, B and F, one injection preferably over deltoid muscle at Day 0 and Week 4. For Study Groups E and I, two injections with each injection over a different deltoid or lateral quadriceps, preferably over the deltoid muscles, at Day 0 and Week 4.
- j. For Study Groups C and G, one injection preferably over deltoid muscle at Day 0 and Week 8. For Study Groups D and H, two injections with each injection over a different deltoid or lateral quadriceps, preferably over the deltoid muscles, at Day 0 and Week 8.
- k. Complete only for Study Groups A, B, E, F and I.
- l. Complete for Study Groups C, D, G and H.
- m. Following administration of INO-4700 or placebo, EP data will be downloaded from the CELLECTRA™ 2000 device and provided to Inovio.
- n. Includes AEs from the time of consent and all injection site reactions that qualify as an AE.
- o. 4 x 8.0 mL (32 mL) whole blood in Cell Preparation Tubes (CPT) per time point. Note: At the investigator's discretion, rather than collecting a sample at screening, 64 mL (8 x 8.0 mL whole blood in CPT tubes) may be collected prior to dosing on Day 0.
- p. 1 x 8 mL blood in 10 mL red top serum collection tube per time point. Note: Collect four aliquots of 1 mL each (total 4 mL) serum at each time point prior to 1st dose. At the investigator's discretion, rather than collecting a sample at screening, 2 x 8 mL blood in two (2) 10 mL red top serum collection tubes (for eight aliquots of 1 mL each) may be collected prior to dosing on Day 0.

TABLE 5 – PART 2 TRIAL SCHEDULE OF EVENTS (DAY 0 & WEEK 4 OPTIMAL REGIMEN)

Tests and assessments	Screen ^a	Day 0		Week 2 (± 3d)	Week 4 (± 5d)		Week 6 (± 5d)	Week 8 ^b (± 5d)	Week 12 (± 5d)	Week 30 ^b (± 10d)	Week 48 (± 5d)		Week 50 ⁱ (± 5d)	Week 68 ⁱ (± 10d)
		Pre	Post		Pre	Post					Pre	Post		
		X												
Informed Consent														
Inclusion/Exclusion Criteria	X													
Medical history	X	X ^a												
Demographics	X													
Concomitant Medications	X	X		X	X		X				X		X	X
Physical Exam ^c	X	X		X	X		X				X		X	X
Vital Signs	X	X		X	X		X				X		X	X
Height and Weight	X													
CBC with differential	X			X			X				X		X	X
Chemistry and Liver Function ^d	X			X			X				X		X	X
Serology ^e	X													
12-lead ECG	X													

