8.5.6 INTERIM ANALYSES

No formal interim analyses will be performed for this trial. However, safety and tolerability will be assessed by the DSMB as noted above for the participants in each Study Group.

A Sponsor unblinded review of the week 10 immunogenicity and safety data will be made during Part 1 of this study when all evaluable data observations are available in order to determine the optimal dose for the Part 2 of the study. The selection of the optimal dose for Part 2 will involve consideration of weighted ordered criteria described in [Figure 3](#) below.

Figure 3: Weighted Ordered Dose Selection Criteria

At a minimum, the optimal selected dose will have a 70% overall immune response and acceptable safety profile as determined by the DSMB and Inovio Medical Council. Other criteria listed in [Figure 3](#) will contribute to the selection of the right optimal dose if the overall immune responses and safety profiles are similar between the Study Groups in Part 1.

A group-level unblinded review of the immunogenicity and safety data will be made once week 12 visit data are complete for all participants in Part 2 whilst maintaining subject-level blinding. Long-term follow-up data will continue to be collected for all participants with remaining visits through to the final visit. These summaries and analyses will allow the Sponsor and collaborators to have results with respect to the immunogenicity and safety endpoints up to and including the Part 2 Week 12 visit on which to inform product development goals. No subject-level immunogenicity data will be produced and subject-level immunogenicity data will not be available in the clinical trial database until all other clinical trial data are finalized at the end of the trial. Thus, Part 2 of the trial will remain blinded to the Sponsor and collaborators with respect to subject treatment assignment.

In order to protect the blind, for the group-level unblinded review, no safety analysis will be provided if the total of subjects who experience the event of interest is greater than 0

and the count of these events relative to the total count of events produces a percentage less than 3% for a given analysis.

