8.5.9 EXPLORATORY ANALYSES

T and B post baseline cell number will be analyzed descriptively by Study Group using the mean or median and associated 95% confidence intervals.

In Part 2, treatment difference comparisons will include a comparison of two dose INO-4700 participants who are boosted with INO-4700 versus two dose INO-4700 participants who are boosted with placebo.

Exploratory ANCOVA and Logistic models may be fit that include baseline, confounder variables such as age, antibodies to other coronaviruses and gender to test the relationship between study group and different immune response variables. The relationship between antibodies to other coronaviruses and humoral immune responses will be explored using regression methods such as linear regression.

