2. PARTICIPANT POPULATION

2.1. Population Definitions

The following participant populations will be used for presentation and analysis of the data:

- The modified intention to treat (mITT) population - includes all participants who receive at least one dose of the INO-4700 or placebo. Participants in this sample will be analyzed by their original assigned dose of INO-4700 or placebo. The mITT population will be used to analyze co-primary and exploratory immunological endpoints.
- The per-protocol (PP) population - comprises mITT participants who receive all their planned administrations and who have no Medical Monitor-assessed important protocol violations. Analyses on the PP population will be considered supportive of the corresponding mITT analyses. Participants excluded from the PP population will be identified and documented prior to locking the study database.
- The safety population (SP) - includes all participants who receive at least one dose of INO-4700 or placebo administered by ID injection. Participants for this population will be grouped in accordance with the dose of INO-4700 or placebo that they received. This population will be used for all safety analyses in the study.

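### Other vaccines are allowed after Week 6 in the Week 4 schedule groups but only after Week 10 in the Week 8 groups, while selection reads Week 10 in all groups and no planned analysis of the responder rate allows for this

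*Protocol*

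**What the plan says.** Protocol v2.0, section 6.4.8, opens the restriction with "Participants must not be vaccinated (e.g., influenza vaccine, COVID-19 vaccine) from 30 days prior to Day 0" and ends it after the visit two weeks after dose 2, which it spells out as "the Week 6 visit if the second dose is at Week 4 and the Week 10 visit if the second dose" is at Week 8. Footnotes k and l to Table 4 give the schedules: the Week 4 dosing procedures are marked "Complete only for Study Groups A, B, E, F and I" and the Week 8 procedures "Complete for Study Groups C, D, G and H".

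Part 1 immunology samples are drawn at Weeks 6 and 10 in all groups (section 3.6). Selection does not vary by schedule: "A Sponsor unblinded review of the week 10 immunogenicity and safety data will be made during Part 1" (section 8.5.6), with a minimum 70% overall immune response for the chosen regimen. Protocol section 8.5.2 and SAP section 4.3.1 add differences in responder percentage between all pairs of active groups and name no other visit for them. A responder is anyone with a rise over baseline in antibody titer or in IFN-gamma-secreting cells, with no fold threshold given (section 6.4.6).

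On related antibodies, section 8.5.9 allows exploratory models with "confounder variables such as age, antibodies to other coronaviruses and gender", and commits to exploring how antibodies to other coronaviruses relate to humoral response. SAP section 4.3.1 also has those antibodies analysed by study group. The per-protocol set removes only participants who fail the condition "who have no Medical Monitor-assessed important protocol violations" or who miss planned doses (SAP section 2.1).

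**The concern.** The vaccine-free period is tied to dose 2, but the decision is tied to a common study week. In A, B and E (and placebo F and I) a non-study vaccine may be given between the Week 6 and Week 10 visits. In C and D (and placebo G and H) it may not be given until the Week 10 visit is complete.

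If such a vaccine moved the MERS-CoV readout, it would do so in one schedule only. It could then enter the response rates that are compared across schedules and set against the 70% minimum. The exposure was foreseeable: the v2.0 summary of changes gives the expected availability of COVID-19 vaccine as the reason for rewriting this restriction. The plan itself regards antibodies to other coronaviruses as a possible confounder and has an exploratory objective on cross-reactivity.

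**Working it through.** **The plan's own figures.** The plan gives no figure for this point, and Part 1 has no power calculation. The one power statement for the endpoint is for Part 2: 260 evaluable, 70% against 80%, one-sided 0.025. It reproduces, with a critical value of 197/260, exact type 1 error 0.0232 and exact power 96.0%, in line with the stated figure of more than 90%. Nothing below depends on it.

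**Step 1: the exposed interval.**
- Nominal, A/B/E: Week 10 minus Week 6 = 70 − 42 = 28 days.
- With visit windows (Week 6 is counted from the Week 4 dose, ±5 days at each visit), the shortest gap is (70 − 5) − (28 + 5 + 14 + 5) = 13 days. The longest is (70 + 5) − (28 − 5 + 14 − 5) = 43 days.
- C/D: 0 days, because the restriction runs until the Week 10 visit is complete.

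**Step 2: does any rule act on a vaccine given in that interval?**
- It is permitted, so it is not a violation. The participant stays in mITT and per-protocol.
- SAP section 3.11 tabulates by the recorded visit, so the result counts as Week 10.
- SAP section 4.3.1 has no rule that excludes, flags or adjusts the responder result.
- The by-group analysis of other-coronavirus antibodies and the exploratory regressions sit beside the responder rate and do not alter it.

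**Step 3: what an effect of a given size would do.** Let p be the true response rate and q the share of true non-responders who become responders because of a permitted vaccine. The observed rate is then p′ = p + (1 − p)q. The documents give no value for q. It is an assumption and may be zero. It can be read as q = v × c, where v is the share vaccinated between the two visits and c is the chance that a vaccinated non-responder converts. For example, 20% × 50% = 10% and 40% × 50% = 20%.

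The 70% minimum with 32 per group needs 0.70 × 32 = 22.4, so 23 responders. The chance of reaching it is the sum over x = 23 to 32 of C(32, x) p′^x (1 − p′)^(32 − x). The last column is the exact chance that a Week 4 group at p′ has more responders than an equally good Week 8 group at p, 32 in each.

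| p | q | p′ | Chance of ≥ 23/32 | Chance of outranking a Week 8 group |
|---|---|---|---|---|
| 60% | 0 | 60% | 11.6% | 44.9% (tie 10.1%) |
| 60% | 5% | 62% | 16.7% | 51.5% |
| 60% | 10% | 64% | 23.1% | 58.0% |
| 60% | 20% | 68% | 39.8% | 70.6% |
| 60% | 30% | 72% | 59.5% | 81.3% |
| 70% | 0 | 70% | 49.5% | 44.6% |
| 70% | 10% | 73% | 64.4% | 55.1% |
| 70% | 20% | 76% | 77.9% | 65.6% |

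The Week 8 group stays on its q = 0 row throughout. For q from 5% to 30% the added points are 2 to 12 at p = 60%, and 1.5 to 9 at p = 70%.

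**The case against.** **The mechanism is not established.** The responder definition uses vaccine-specific readouts. The documents treat cross-reactivity as an open, exploratory question and for humoral response only, and the assay positivity rules are not in them. A reader might infer that a COVID-19 vaccine will raise MERS-CoV responses, including the IFN-gamma count. The documents do not support that, and the cellular route has no basis in them at all. This stands, so the sizes above are illustrations.

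**The plan is not blind to the issue.** Other-coronavirus antibodies are analysed by group, their relation to humoral response will be explored, and the optional logistic models could take responder status as the outcome. That is fair credit. It could reveal differential exposure, but it leaves the responder rate, the 70% minimum and the pairwise differences as they are.

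**There are partial internal checks.** Placebo groups F and I share the early end of the restriction, and response rates are reported within each group. They total 16 people; at q = 10% that is 1.6 expected conversions, too few to correct a rate. A Week 6 sample exists in A, B and E, and the protocol's phrasing for selection leaves the responder time point loose. A rule counting a response at any visit would still include Week 10.

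**The direction is mixed.** A reader might infer that the gap always favours the Week 4 schedule. Reactions to another vaccine would also count as TEAEs in A, B and E and weigh against those groups. The planned Part 1 comparison with placebo is limited to related SAEs and related Grade 3 or higher events, and relatedness takes alternative causes into account, so the safety effect may be small.

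**The outcome.** A reader might infer that a wrong regimen was chosen. The administrative memo discontinuing Part 2 says no group met the selection criteria on the Week 10 results, so upward inflation caused no wrong selection. Nor does the point extend usefully to Part 2, which carries one regimen and was not run.

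**Conclusion.** The asymmetry is in the text and needs no assumption: up to a nominal 28 days of permitted exposure before the deciding sample in A, B and E, and none in C and D, with no rule for it in the responder analysis. Whether it biases anything, and by how much, cannot be settled from the documents. On a true rate of 60%, an assumed 4 points takes the chance of meeting the minimum from 12% to 23%, and 8 points takes it to 40%; with q = 0 nothing changes.

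What remains exposed is the descriptive comparison of schedules. The memo says Week 48 samples will not be analysed, so under v2.0 Weeks 6 and 10 are the only scheduled post-dose immunology results left. Confidence is moderate, and the point is worth acting on mainly because the remedy is cheap.

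**What to change.** Leave the vaccine rule to the sponsor, who should reconcile the end of the restriction in section 6.4.8 with the common Week 10 assessment. In SAP section 4.3.1, keep the Week 10 analysis and pre-specify two Part 1 sensitivity analyses of the overall response rate (against the 70% minimum) and of the pairwise differences:

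- **(a)** Exclude immunology results drawn after receipt of any non-study vaccine, removing the participant from numerator and denominator at that visit. Concomitant medications are reviewed at Weeks 8 and 10 in Part 1 and recorded with dates (section 6.4.7). This assumes vaccines are entered there.
- **(b)** Compare all groups two weeks after dose 2: Week 6 for A, B and E, and Week 10 for C and D. Every group is then still inside the restriction.

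Report by group the number vaccinated before the Week 10 sample, and flag TEAEs with onset after a non-study vaccine.

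Replacing Week 10 by Week 6 only in vaccinated A, B and E participants is not advised as the main analysis. It would mix two-week and six-week post-dose results within a group, and it sits badly with the rule against replacing missing data.

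The cost is SAP wording and one or two tables. Analysis (a) loses a few samples. Analysis (b) does not compare groups at the same study week, and it changes time since dose 2 as well as vaccine exposure, so a shift in (b) alone should not be put down to vaccination.

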7.0 EVALUATION OF SAFETY AND MANAGEMENT OF TOXICITY

7.1 SAFETY PARAMETERS

The safety of INO-4700 will be measured and graded in accordance with the “Toxicity Grading Scale for Healthy Adult and Adolescent Volunteers Enrolled in Preventive Vaccine Clinical Trials”, issued September 2007 ([Appendix A](#)).

7.2 ADVERSE EVENTS (AEs)

Any untoward medical occurrence in a patient or clinical investigation subject administered a pharmaceutical product and which does not necessarily have to have a causal relationship with this treatment.

An AE can therefore be any unfavorable and unintended sign (including an abnormal laboratory finding, for example), symptom, or disease temporally associated with the use of a medicinal product, whether or not considered related to the medicinal product.

Adverse Events (AEs) include the following:

- Pre- or post-treatment complications that occur as a result of protocol mandated procedure during or after screening (before the administration of clinical trial drug)
- Any pre-existing condition that increases in severity, or changes in nature during or as a consequence of the clinical trial drug administration phase
- Complications of pregnancy (refer to [Section 7.11](#))

Adverse Events (AEs) do not include the following:

- Medical or surgical procedures (e.g., surgery, endoscopy, tooth extraction, transfusion) performed; however, the condition that leads to the procedure is an AE
- Pre-existing diseases or conditions or laboratory abnormalities present or detected before the Screening Visit that do not worsen
- Situations where an untoward medical occurrence has not occurred (e.g., hospitalization for elective surgery, social and/or convenience admissions)
- Overdose without clinical sequelae
- Any medical condition or clinically significant laboratory abnormality with an onset date before the ICF is signed, is not an AE; it is considered to be pre-existing and will be documented on the medical history CRF
- Uncomplicated pregnancy
- An induced elective abortion to terminate a pregnancy without medical reason

7.3 ADVERSE DRUG REACTION (ADR)

All noxious and unintended responses to a medicinal product related to any dose. This means that a causal relationship between the medicinal product and an adverse event is at least a reasonable possibility (i.e., the relationship cannot be ruled out).

7.4 SERIOUS ADVERSE EVENTS (SAEs)

An SAE is any untoward medical occurrence that at any dose:

- Results in death
- Is life-threatening
 - Refers to an event in which the participant was at risk of death at the time of the event. It does not refer to an event which hypothetically might have caused death if it were more severe.
- Requires inpatient hospitalization or prolongation of existing hospitalization
 - Includes any hospitalization in which the participant has been admitted to the hospital regardless the length of stay, even if the hospitalization is only a precautionary measure to allow continued observation. However, hospitalization (including hospitalization for an elective procedure) for a pre-existing condition that has not worsened, does not constitute an SAE.
- Results in persistent or significant disability/incapacity
 - A substantial disruption of a person's ability to conduct normal life functions (i.e., the adverse event resulted in a significant, persistent or permanent change, impairment, damage or disruption in the participant's body function/structure, physical activities and/or quality of life).
- Results in congenital anomaly or birth defect and/or
- An important medical event
 - An event that may not be immediately life-threatening or result in death or hospitalization but may jeopardize the participant or may require intervention to prevent one of the other outcomes listed above. Examples of such events are intensive treatment in an emergency room or at home for allergic bronchospasm, blood dyscrasias or convulsions that do not result in hospitalization, or development of drug dependency or drug abuse.

Clarification of Serious Adverse Events (SAEs)

- Death in itself is not an AE. Death is an outcome of an AE, but when the cause of death has not been provided, use the event term: death of unknown cause.
- The participant may not have been receiving an investigational medicinal product at the occurrence of the event.
- Complications that occur during hospitalizations are AEs. If a complication prolongs the hospitalization, it is an SAE.

7.5 UNEXPECTED ADVERSE DRUG REACTION

An adverse reaction, the nature or severity of which is not consistent with the applicable product information (e.g., Investigator's Brochure [IB] for an unapproved investigational product, package insert/summary of product characteristics for an approved product).

7.6 UNANTICIPATED (SERIOUS) ADVERSE DEVICE EFFECT (UADE)

A UADE is any serious adverse effect on health or safety or any life-threatening problem or death caused by, or associated with, a device, if that effect, problem, or death was not previously identified in nature, severity, or degree of incidence in the investigational plan or application (including a supplementary plan or application), or any other unanticipated serious problem associated with a device that relates to the rights, safety, or welfare of participants.

A UADE is a type of SAE that requires reporting to the Sponsor in accordance with [Section 7.9](#).

7.7 DEVICE DEFICIENCY

A device deficiency is an inadequacy of a medical device with respect to its identity, quality, durability, reliability, safety or performance.

Note: Device deficiencies include malfunctions, use errors and inadequate labelling.

